### 6.3.3. Electrocardiogram

Statistical analyses of ECG parameters will be performed by [REDACTED]. These analyses will be defined in a separate statistical analysis plan, written by [REDACTED]

### 6.3.4. Other safety endpoints

- Number of patients who discontinued treatment for safety reason\*,

DNDi-FEX-09-HAT (DNDi)	Statistical Analysis Plan Version 3.0 – 30/09/2022	Page 12 / 37
------------------------	---	--------------

- Number of patients who were hospitalized for reasons related to safety\*, including overdose.

\* Reasons collected in the CRF comments will be classified by a medical review as "safety reason" or "other reason".

## 6.4. Other endpoints and variables

### 6.4.1. Demographic and other baseline characteristics

The following standard characteristics (gender, BMI, etc.) will be used as recorded in the CRF:

- Demographic characteristics
- Vital signs at baseline
- Clinical signs and symptoms of HAT at baseline
- Physical examination at baseline
- Neurological examination at baseline
- HAT diagnosis (i.e. examination of blood, lymph and CSF samples)

The following data will be derived:

- Age (years) will be used as collected in eCRF. If not available then it will be calculated as the exact duration in years between date of birth and date of informed consent
- BMI classified according to the World Health Organization (WHO):
  - <18.5 – Underweight
  - 18.5 - <25 – Normal weight
  - 25 - <30 – Overweight
  - ≥30 – Obesity

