A study on fexinidazole concentrations in milk was conducted on lactating female albino rats after the administration of 800 mgeq/kg of [14C]-fexinidazole. Radioactive drug-related material was detected in milk at a concentration similar to that in plasma and in blood. Exposure to the radioactive drug-related material was approximately 80% of that measured in plasma, in terms of both C_{max} and AUC values.

On the basis of these findings, the same extent of exposure can be expected in breastfed human newborns. Median and maximum plasma exposure to M2, the main metabolite, observed in women participating in the FEX004 study were 529 and 930 μ g•h/mL respectively. This corresponds to a plasma M2 concentration of approximately 22 to 39 μ g/mL, from which it can be inferred that the concentration in breast milk will be from 18 to 31 μ g/mL. Thus, for newborns with a mean weight

Confidential Page 22 of 83

of 3 kg who consume around 500 mL of breast milk per day, this corresponds to total exposure to M2 in the range of 9.0 to 15.5 mg/day, i.e. 3.0 to 5.2 mg/kg.

Nevertheless, as a precautionary measure, pregnant women will be eligible to participate in the study only once they have reached the second trimester of pregnancy and will not be eligible for treatment on an out-patient basis.

The target population will also include patients whose health status is not as good as in earlier studies, within medically acceptable limits, as this is likely to be the case for some patients who will be treated in the future. Thus, the eligibility criteria for patients in the study are less strict that those in earlier studies on fexinidazole with, in particular, deletion of some criteria based on laboratory tests and on bodymass index (BMI).

As in early studies, in particular DNDiHATFEX006, children under 6 years of age will not be part of the target population for practical reasons related to the size of the tablets and difficulty in swallowing them.

Lastly, the study will provide additional laboratory data at 3 months and 6 months to supplement the existing laboratory safety database, with a particular focus on haematological and hepatic functions.

2. Study Objectives and Endpoints

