2.2.6. Secondary Endpoints - PK

The secondary endpoint for the PK assessment will be:

 PK parameters of fexinidazole and its metabolites in whole blood, measured in all patients treated in hospital.

3. Study Design

This is a prospective, multicentre, open-label study, assessing the effectiveness of fexinidazole in a cohort of adults and children with HAT at any stage, with follow-up over 18 months.

It is planned to include 174 patients in 4 investigational centres or more in the DRC and in Guinea that have experience in the treatment of patients with HAT.

Confidential Page 25 of 83

The duration of treatment is 10 days. Patients will be treated on an out-patient basis or in hospital, in accordance with pre-set inclusion and non-inclusion criteria.

The end of study corresponds to the last visit of the last patient.

4. Eligibility Criteria

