4.1. Inclusion Criteria

To be included in the study, the patient must fulfil all of the following criteria:

- Male or female patient, including breastfeeding or pregnant women in the second or third trimester;
- ≥ 6 years of age;
- ≥ 20 kg body weight;
- Signed Informed Consent Form and Assent Form for patients less than 18 years of age;
- Trypanosomes detected in any body fluid;
- Physically able to ingest at least one solid meal per day;
- Able to take oral medication;
- Karnofsky Performance Status > 40% (see Appendix 2 Performance Status Scale, p74);
- Able to comply with the schedule of follow-up visits and with the study constraints;
- Easily reachable during the out-patient follow-up period;
- Willing to undergo lumbar punctures.

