5.1. Investigational Medicinal Product

The investigational medicinal product (IMP) is fexinidazole as 600-mg tablets, to be taken orally in a single intake during the main meal of the day at the daily dose of:

Adult patients and children with body weight equal to or above 35 kg:

- 1800 mg (3 tablets) for 4 days, followed by
- 1200 mg (2 tablets) for 6 days.

Children with body weight of at least 20 kg and below 35 kg:

- 1200 mg (2 tablets) for 4 days, followed by
- 600 mg (1 tablets) for 6 days.

The total duration of treatment will be 10 days.

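### SAP 6.4.1 applies one fixed set of BMI classes, with no age condition, to a population that includes children from 6 years and 20 kg

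*SAP*

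**What the plan says.** SAP 6.4.1 lists the variables to be derived for the baseline description. One is "BMI classified according to the World Health Organization (WHO"). The lowest class is "<18.5 – Underweight", the next is "18.5 - <25 – Normal weight", and two higher classes follow, cut at 25 and 30. No age or sex condition is attached. The same section also uses BMI itself as a characteristic recorded in the CRF.

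The population includes children. Protocol section 4.1 admits patients at "≥ 6 years of age" and "≥ 20 kg body weight", and section 3 describes a study "in a cohort of adults and children with HAT at any stage". Section 5.1 has a separate weight band: "Children with body weight of at least 20 kg and below 35 kg".

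SAP 8.4 describes baseline data on the mITT population by cohort, by subgroup and overall. The subgroups in SAP section 5 are defined by disease stage and CSF white cell count only. Table 1.4.1 in the SAP's list of outputs is a single demographic table. None of these separates children from adults.

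Protocol section 1.6 explains that eligibility is less strict than in earlier fexinidazole studies, with "deletion of some criteria based on laboratory tests and on bodymass index (BMI").

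**The concern.** BMI is weight divided by height squared, and it changes as a child grows. A fixed lower limit of 18.5 that may suit adults therefore sorts young children largely by age. A child of ordinary build for age and a malnourished child can receive the same label.

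This has some descriptive weight here. The protocol widened eligibility partly by dropping BMI-based criteria, so a reader may turn to the BMI classes to see what population resulted. A pooled underweight percentage cannot answer that, because it moves with the share of children as well as with nutrition.

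The comparison of columns has the same weakness. Protocol section 4.3 bars pregnant and breastfeeding women and patients with neurological symptoms from out-patient treatment, so the age mix of the two cohorts may differ by design. A difference in the underweight percentage between in-patients and out-patients, or between stages, could then be partly a difference in age.

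**Working it through.** The plan gives no figure on this point to reproduce, so the check is what the stated rule does to the patients whom the protocol admits.

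**Step 1. Height above which a patient is classed underweight.** Inputs: the cut-off of 18.5 (SAP 6.4.1), the minimum weight of 20 kg (Protocol 4.1) and the upper limit of the children's band, below 35 kg (Protocol 5.1). BMI = w/h², so BMI < 18.5 exactly when h > √(w/18.5).

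- 20 kg: √(20/18.5) = 1.040 m
- 25 kg: √(25/18.5) = 1.162 m
- 30 kg: √(30/18.5) = 1.273 m
- 34.9 kg: √(34.9/18.5) = 1.373 m
- 45 kg: √(45/18.5) = 1.560 m
- 55 kg: √(55/18.5) = 1.724 m

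Within the children's band, only a child who is short for the given weight reaches the normal class. At adolescent weights the limit is much less restrictive.

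**Step 2. Share of a group falling below 18.5.** The documents give no heights and no BMI distribution, so this step is an assumption. Take BMI as log-normal with median m and a coefficient of variation (CV) of 8-14%, used as the log-scale SD. The share is Φ(ln(18.5/m)/CV).

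| Assumed median BMI | Share classed underweight |
|---|---|
| 14.5 | 96-100% |
| 15.5 | 90-99% |
| 16.5 | 79-92% |
| 17.5 | 65-76% |
| 18.5 | 50% |
| 19.5 | 26-35% |
| 20.5 | 10-23% |

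Example: for m = 15.5, ln(18.5/15.5) = 0.177. Dividing by 0.08 gives 2.21 (99%), and dividing by 0.14 gives 1.26 (90%).

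**Step 3. Effect on the pooled percentage.** Let c be the share of children, u the share of children classed underweight and a the share of adults so classed. The pooled percentage is (1 − c)a + cu, so it exceeds the adult percentage by c(u − a). None of c, u or a is in the documents. Assume u = 60-95% and a = 15-30%.

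- c = 5%: from 0.05 × (60 − 30) = 1.5 to 0.05 × (95 − 15) = 4 points
- c = 10%: from 0.10 × 30 = 3 to 0.10 × 80 = 8 points
- c = 15%: from 0.15 × 30 = 4.5 to 0.15 × 80 = 12 points
- c = 20%: from 0.20 × 30 = 6 to 0.20 × 80 = 16 points

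At c = 15% of the planned 174 patients, about 26 are children (0.15 × 174 = 26.1).

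**Step 4. Where else the classes are used.** They do not appear in the eligibility criteria, the analysis sets or subgroups (SAP section 5), the failure models (SAP 8.7.2), the outcome algorithms (SAP section 10) or the sample-size calculation (Protocol 9.1).

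**The case against.** The strongest reply is that this is one derived categorical row. BMI as recorded is also described, and under SAP 7.4 a quantitative variable gets its mean, SD, median, quartiles and range. Age is reported, and patient characteristics are listed individually, so a careful reader could recover the picture. This stands, and it keeps the point minor. It does not make the row correct.

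Four stronger readings are tempting, and the documents do not support them.

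- A reader might infer that almost every child will be called underweight. Step 2 gives that only for a group with median BMI of about 15.5 or less. Patients under 18 include adolescents and children of 35 kg or more, and at a median of 18.5 the share is one half.
- A reader might infer that the baseline description as a whole is wrong. Only the class row is affected.
- A reader might infer false nutritional differences between centres. The SAP plans results by centre for success rates only; no table of BMI by centre is planned.
- A reader might infer that the protocol undertakes to measure its relaxed criteria by BMI class. Section 1.6 only says that some criteria were dropped, and Protocol 9.4 does not name BMI.

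Two further reservations stand. The documents do not label the four cut-offs as adult ones; that, and the dependence of BMI on age in childhood, are general knowledge. The protocol's baseline procedures also do not name height, so it is not established that the recorded data support a BMI-for-age score.

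**Conclusion.** The point holds as a minor error in a stated rule. Followed as written, SAP 6.4.1 puts children from 6 years on the same fixed scale as adults. Many younger children would be classed underweight whatever their status for age, and the underweight percentages overall, by cohort and by stage would mix nutrition with the share of children.

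The height limits in step 1 follow from the documents alone. The size of the effect does not. The 4.5 to 12 points assume 15% children, 60-95% of them in the class and 15-30% of adults in it. That excess is also not pure misclassification, since some children may be truly thin for their age. With few children enrolled, the effect would be small.

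**What to change.** In SAP 6.4.1, limit the four BMI classes to patients aged 18 or over. In Table 1.4.1, show patients under 18 in a separate block. A BMI-for-age classification is preferable there, if the recorded age, gender and BMI allow it; otherwise give continuous BMI by age band. State the number of patients in each block, so that the reader can see the share of children in every column.

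The protocol already accepts group-specific limits where a single limit would mislead: the adapted haemoglobin grades in its Appendix 6 differ for men and women.

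The cost is one age condition and one extra block in one table, plus a reference table if BMI-for-age is used. No endpoint, analysis set or stated figure changes. Because the classes are purely descriptive, the correction carries no risk of bias to the efficacy or safety results, even after database lock.

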### 6.4.2. Medical history

Medical and surgical history will be coded using MedDRA dictionary (last available version at the beginning of the coding).

### 6.4.3. Prior and concomitant therapies

Prior and concomitant therapies will be coded with WHO-Drug Dictionary September 2013 C-format.

- Prior therapies are therapies which stopped before the first study drug administration.
- Concomitant therapies are therapies which ended on or after the first study drug administration or are ongoing at the end of the trial.

### 6.4.4. Extent of exposure

Extent of exposure will be derived as follows:

- Extent of exposure (days) = Date of last study drug administration - Date of first study drug administration + 1

## 7. DATA ANALYSIS CONSIDERATIONS

### 7.1. Statistical software

The statistical analysis will be performed using SAS® software v9.4 (or a later version).

### 7.2. Type I error

For all analyses, the type I error ( $\alpha$ ) is set to 0.05 two-sided.

### 7.3. Centre effect

The primary analysis will not be stratified by centre because the weight of each centre in the overall population is unknown. Nevertheless, the results by centre for each cohort will be presented and a test of homogeneity (a likelihood-ratio test) will be performed on the success rates. A centre effect is possible. In this case, an estimate of the overall success rate will also be provided, giving equal weight to each centre rather than weighting the centres based on the number of treated patients. The estimate of the rate will be given by  $p = \sum W_h p_h$  where  $W_h$  is the weight of each centre, i.e. the inverse of the number ( $h$ ) of centres ( $1/h$ ). The variance of the estimator will be equal to  $\text{Var}(P_h) = \sum W_h^2 \cdot p_h(1-p_h) / n_h$  where  $n_h$  is the number of patients in centre  $h$ . In addition, a Forest plot will be presented to assess whether the heterogeneity is quantitative (dispersion around a central value) or qualitative (presence of very atypical centres).

### 7.4. Descriptive analyses of quantitative and qualitative variables

Quantitative variables will be described by: N (number of patients with non-missing data), missing (number of patients with missing data), mean, standard deviation (SD), minimum, maximum, median, first quartile (Q1) and third quartile (Q3).

Categorical variables will be described by frequency and percentage of patients in each category. Percentages will be expressed with one decimal place. The Clopper-Pearson (exact) 95% confidence interval will be provided, if required in [Section 8](#).

### 7.5. Definition of baseline, time-windows and analysis periods

#### Baseline:

Baseline is defined by data collected during the D-15 to D-1 period before the beginning of the treatment.

#### Analysis periods:

Study procedures will be performed in accordance with the following schedule:

- Between D-15 to D-1: screening and baseline assessment,
- D0: IMP dispensing visit prior to first intake of IMP (Patients on an outpatient basis only)
- D1 to D10: treatment period,
- D11: End of Treatment (EoT) visit
- Between D13 to D18 : End of Hospitalization (EoH) visit (Patients treated in hospital only)

Follow-up visits for all patients will be performed at 3 months, 6 months, 12 months and 18 months.

#### Time-windows:

The timing of follow-up visits is calculated from the first day of treatment (D1).

The table below defines the theoretical schedule of follow-up visits and the acceptable Leeway:

Type of visit	Schedule of visit and ideal timing of visits	Acceptable Leeway*
End-of-hospitalisation (EoH) visit, only for patients treated in hospital	Between D13 and D18 after D1	D18 at the latest
3 months	3 months $\pm$ 1 week after D1	2 to 4 months, i.e. 60 to 149 days, after Day 1
6 months	6 months $\pm$ 1 weeks after D1	5 to 9 months, i.e. 150 to 299 days, after Day 1
12 months	12 months $\pm$ 4 weeks after D1	10 to 16 months, i.e. 300 to 509 days, after Day 1
18 months	18 months $\pm$ 4 weeks after D1	17 to 21 months, i.e. 510 to 659 days, after Day 1

\* The acceptable leeway for the visit starts on the first day of the period mentioned and ends on the last day of the period mentioned.

Any additional unscheduled visits that may take place must be recorded in the CRF. Real timing of unscheduled visits will be calculated and they will be analysed in the corresponding time-window (see table above).

## 7.6. Handling of missing data and outliers

### Handling of missing data for primary and secondary efficacy endpoints:

Handling of missing data is described in Section 9.8 of the Protocol and is included in the derivation algorithms for outcome at 18 and 12 months (cf. [Section 10](#)).

### Handling of missing AE attributes:

Missing relationship, missing seriousness, and/or missing severity will not be replaced and will be analysed as such.

Onset date of AE will be imputed as below. The general rule in the absence of information is to retain a conservative imputation.

Onset date of AE	Imputed AE onset date
Completely missing	For AEs collected in the “Screening” form: Date of informed consent For AEs collected in the “Follow-up” forms: Date of first study drug administration
Day is missing	First day of the month. For AEs collected in the “Screening” form: If imputed date is prior to date of informed consent, then replace with date of informed consent. For AEs collected in the “Follow-up” forms:

Onset date of AE	Imputed AE onset date
Day and month are missing	
If imputed date is prior to date of first study drug administration, then replace with date of first study drug administration.
 
First of January.
 
For AEs collected in the “Screening” form:
 
If imputed date is prior to date of informed consent, then replace with date of informed consent.
 
For AEs collected in the “Follow-up” forms:
 
If imputed date is prior to first study drug administration, then replace with date of first study drug administration.

	
Note: partially or completely missing end dates of AE will not be imputed.

**Handling of missing stop dates of prior and concomitant therapies:**

For therapies marked as “ongoing”: the stop date will not be imputed.

For therapies marked as “not ongoing”, the stop date will be imputed as below.

Stop date of therapy	Imputed stop date
Completely missing	No imputation. The therapy will be considered as “ongoing” for the analysis.
Day is missing	
Last day of the month.
 
For therapy collected in the “Screening” form: if imputed date is later than the end of hospitalisation visit date, then replace with the end of hospitalisation visit date.
 
For therapy collected in the “Follow-up” form: if imputed date is later than the date of last contact, then replace with the date of last contact.

Day and month are missing	
31 December
 
For therapy collected in the “Screening” form: if imputed date is later than the end of hospitalisation visit date, then replace with the end of hospitalisation visit date.
 
For therapy collected in the “Follow-up” form: if imputed date is later than the date of last contact, then replace with the date of last contact.

Note: partially or completely missing start dates of therapies will not be imputed.

## 8. PLANNED STATISTICAL ANALYSES

### 8.1. Disposition of patients

Disposition of patients and reasons for premature discontinuations will be tabulated overall, by cohorts (i.e. “inpatients” and “outpatients”) and in each subgroups defined in [Section 5](#) (i.e. “Stage 1”, “Intermediate stage”, “Stage 1 + intermediate stage” and “Stage 2”):

- Number of screened HAT positive patients (i.e. patients who gave informed consent)
- Amongst screened HAT positive patients:
  - Number and percentage of patients who attended the dispensation visit (i.e. Day 0), for “inpatients”
  - Number and percentage of patients who attended visit “Day 1”, for “outpatients”
- Number of patients included (i.e. which meets all the criteria for inclusion and has no exclusion criteria)
- Number of patients treated (i.e. who received at least one tablet of fexinidazole)
- Amongst treated patients:
  - Number and percentage of patients who withdrew from the study prematurely, listed by reason for withdrawal
  - Number and percentage of patients who completed the trial according to the protocol
- The following data will also be provided amongst treated patients:
  - Number and percentage of patients who received all of the protocol-planned doses (=treatment completers)
  - Number and percentage of patients who died for reasons clearly unrelated to the IP or HAT
  - Number and percentage of patients who had at least one minor protocol violation
  - Number and percentage of patients who had at least one major protocol violation
  - Number and percentage of patients who underwent lumbar puncture at the end-of-hospitalisation, at the 3-month visit, at the 6-month visit, the 12-month visit and the 18-month
  - Number and percentage of patients who attended visits “Day 1” to “Day 10” (for inpatients only), the end-of-treatment (EoT) visit, the end-of-hospitalisation (EoH) visit (for inpatients only), the 3-month, 6-month, 12-month and 18-month visits.

In addition the following data will be provided:

- Date of first patient screened
- Date of first administration of the first patient
- Date of first administration of the last patient
- Date of last patient last visit (i.e. last visit performed)
- Study duration (days) = date of last patient last visit - date of first administration of the first patient

## 8.2. Protocol deviations

Minor and major protocol violations will be described separately, by cohort, by subgroups and overall on the mITT.

Protocol violations will be listed and finalised prior to the data review meeting. The sponsor will be responsible for classifying all violations as either major or minor. Patients with at least one major protocol violation will be excluded from the PP set. A specific data review plan will provide a more detailed description on deviation review. All decision taken by the data review members will be reported in the Data review document.

## 8.3. Analysis sets and subgroups

Frequency and percentage of patients included in each analysis sets defined in [Section 5](#) will be provided by cohorts, subgroups and overall.

